Endpoints:	
Stage 1:
 
• Data collection to verify accuracy• Data collection to understand the natural history of flow physiology in AV fistulas and classify fistulas that will fail 
Stage 2:
 
Primary Performance Endpoints:
 
• Rate of successful fistula maturation 
Secondary Performance Endpoints:
 
• Cumulative fistula patency at the end of 1 year• Conduit diameter measurements• Volumetric flow measurements
-------------------	--

Inclusion Criteria	
 • Age > 18 years • Patients presenting for upper extremity autologous arteriovenous fistula creation for hemodialysis access where the surgeon selects EchoMark and EchoSure as an appropriate method of monitoring. • Patient is able to sign informed consent and able to participate in all testing associated with this clinical investigation • Women of childbearing potential have a negative pregnancy test.
Exclusion Criteria	
 • Age <18 years old • Patient unable to sign informed consent • Patient participating in another investigational device or pharmacological study • Prisoner or patient from vulnerable populations as defined in 45 CFR 46.
Follow Up:	Patients will have variable follow up depending on the rate of fistula maturation as well as the follow up required by the surgeon per his or her standard practice.

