5. STUDY OBJECTIVES

Purpose

Stage 1: The primary objective of Stage 1 of the study is to collect data to verify the technology's performance in fistula monitoring. In Stage 1, EchoMark is implanted and monitoring is completed post-operatively. EchoSure data is then captured in an effort to establish normal ranges of the relevant variables in the context of appropriately maturing fistulae and their physiology, which is currently unknown.

Stage 2: The purpose of Stage 2 of the study is to evaluate the performance of the EchoMark and EchoSure (both FDA approved devices) as an ultrasound-based method of monitoring maturation of fistulae. The implant and ultrasound will be used as per IFU. The primary purpose of the study is to collect data on patient outcomes and assess whether or not the information generated from use of

EchoMark and EchoSure can decrease the fistula maturation failure rate and improve the patency of fistulas after up to a year.

Performance Goals

Stage 1:

Primary Performance Endpoint:

- Data collection to verify accuracy
- Data collection to understand the natural history of flow physiology in AV fistulas and classify fistulas that will fail

Primary Safety Endpoint:

- Procedure freedom from Serious Adverse Events (SAEs) during the EchoMark implantation procedure and subsequent post-operative period

Stage 2:

Primary Performance Endpoint:

- Failed fistula maturation rate

Secondary Performance Endpoints:

- Cumulative fistula patency at the end of 1 year
- Volumetric flow data
- Vessel caliber
- Total cost of episode of care

Primary Safety Endpoint:

- Procedure freedom from Serious Adverse Events (SAEs) during the EchoMark implantation procedure and subsequent post-operative care.

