7. STUDY POPULATION

Number of Patients

Stage 1: Up to sixty (60) patients will be enrolled and both men and women will

be eligible for inclusion. The estimated enrollment period is six months and patients will be followed until the fistula matures and is suitable for use in dialysis or it is ultimately considered non-salvageable by the vascular surgeon.

Stage 2: Up to sixty (60) patients will be enrolled and both men and women will be eligible for inclusion. The estimated enrollment period is twelve months and patients will be followed until then or the decision by the attending surgeon that the fistula failure is confirmed, or that monitoring is no longer clinically necessary patients will exit the study.

Intended Use

The EchoMark and EchoSure devices are intended to be used by a trained medical professional. The EchoMark device is intended to be a Single Use Device, used in a surgical operating suite or equivalent setting. The EchoSure ultrasound devices are reusable and may be used in the operating suite, a post-operative unit such as the ICU or patient floor, or a typical outpatient clinic. When used intraoperatively or in the presence of breached skin, the ultrasound transducer should be used with a sterile probe cover.

Inclusion Criteria

- Age > 18 years
- Patients presenting for upper extremity arteriovenous fistula construction with autologous tissue for the purpose of eventual hemodialysis access where the surgeon has selected EchoMark and EchoSure as the optimal method of vascular monitoring based on clinical assessment and plan
- Patient is able to sign informed consent and able to participate in all testing associated with this clinical investigation
- Women of childbearing potential have a negative pregnancy test

Exclusion Criteria

- Age <18 years old
- Patient unable to sign informed consent
- Patient participating in another investigational device or pharmacological study
- Prisoner or patient from vulnerable populations as defined in 45 CFR 46.

This study will not target the recruitment of any potentially vulnerable subjects. If vulnerable subjects who are educationally or economically impaired present for fistula creation, they will not be given the opportunity to participate in the study.

PATIENT WITHDRAWAL FROM THE STUDY

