10. STUDY PROCEDURES AND METHODS

Patients undergoing fistula creation procedures will be identified. The study will be explained to these patients and informed consent for participation in the study will be obtained from willing patients. A small, FDA-approved tissue marker will be implanted prior to closure of wounds following the Instructions for Use on the FDA-approved labelling.

Stage 1: The fistula will be assessed with intermittent EchoSure examinations, sometimes during routine dialysis visits (maximum 3x/week) to minimize travel. This will conclude when the fistula has entirely matured and the patient begins hemodialysis via the fistula or when the vascular surgeon declares that the fistula has failed despite any and all salvage attempts.

Stage 2: Similar to stage 1 but with implementation of the normative values for relevant variables that resulted from the data collected in stage 1, with subsequent use of the EchoSure flow information in the vascular surgeon's decision making. This stage will also conclude when a year has passed and the fistula is functioning or when the vascular surgeon declares that the fistula has failed despite any and all salvage attempts or that monitoring is no longer clinically necessary.

Actions to Be Taken by Site Staff	Screening and pre-operative evaluation	Clinic Visits	Initiation of dialysis or fistula failure
Consenting	X		
Initial Enrollment Form		X	
Nurse Scan Form		X	
EchoSure Scan		X	
Standard Clinical Exam		X	
End of Trial Period Form			X

11: DATA COLLECTION, ANALYSIS, AND MONITORING

Adverse events are not expected in this study. Unanticipated problems will be reported and discussed with the principal investigator and research coordinator. Patients will be regularly monitored for signs of infection, inflammation or device extrusion. Should the implantable device require removal, it will be removed, and patient will be monitored with conventional methods. The research team will periodically review its protocols to ensure maximal patient safety and data validity.

Source Documentation

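### One-year patency is a Stage 2 endpoint, but patients with working fistulas may leave the study early with no later status check, and the projected dates need reconciling

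*Combined protocol and SAP*

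**What the plan says.** Section 3 (Endpoints) lists "Cumulative fistula patency at the end of 1 year" as a Stage 2 secondary endpoint, and Section 5 repeats it. The Section 5 purpose statement for Stage 2 adds the aim to "improve the patency of fistulas after up to a year".

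Follow-up is described in several places:

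- Section 3 (Follow Up): "Patients will have variable follow up depending on the rate of fistula maturation", and also according to the surgeon's standard practice.
- Section 3 (Treatments), second paragraph: monitoring for at most 52 weeks, with exit at confirmed failure or when the surgeon finds monitoring no longer necessary. The paragraph is labelled Stage 1, but its content matches the Stage 2 text elsewhere.
- Section 7 (Number of Patients, Stage 2): an estimated enrolment period of twelve months, follow-up 'until then', and exit at confirmed failure or when the surgeon decides that "monitoring is no longer clinically necessary patients will exit the study".
- Section 10 (Stage 2): "This stage will also conclude when a year has passed and the fistula is functioning". This is joined by 'or' to a fistula declared to have "failed despite any and all salvage attempts", and to monitoring no longer being necessary.
- Section 10 (schedule table): the End of Trial Period Form appears only in the column "Initiation of dialysis or fistula failure". Clinic visits carry no dates.

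Sections 3 and 6 project the whole study from May 2020 to December 2021. Section 7 estimates six months of enrolment for Stage 1. Section 10 runs Stage 2 "with implementation of the normative values for relevant variables that resulted from the data collected in stage 1".

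**The concern.** A one-year patency figure needs each fistula's status at one year, or censoring that is unrelated to prognosis. The Stage 2 exit rule secures neither. It has no minimum time, it applies to fistulas that have not failed, and nothing is planned to establish what happens to them afterwards.

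The surgeon's decision depends on how the fistula looks, so patients who exit may differ in prognosis from those still watched. If they do better, censoring them at exit understates patency. If they are counted as patent, any later loss goes unseen and patency is overstated. Neither simple handling is safe, and status that nobody planned to collect may not be recoverable later.

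The calendar raises a second question. On one natural reading of the enrolment period, the projected window is too short for every Stage 2 patient to have a year of follow-up.

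**Working it through.** **Inputs.** Stage 2 size 60, from 45 with a 25% dropout allowance (Section 8). Maturation success 78% under early ultrasound and intervention (Section 8). Maximum Stage 2 monitoring 52 weeks (Section 3). Enrolment periods of 6 and 12 months (Section 7). Stage 1 monitoring of up to 24 weeks (Section 3). Window May 2020 to December 2021 (Sections 3 and 6). The share of working fistulas that exit early is not in the documents, so a range is shown.

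**The plan's own size.** 45 / (1 - 0.25) = 60, as stated. The 45 also reproduces: a two-sided 5% chi-square test of 50% against 78%, without continuity correction, has 80.1% power with 45 per cohort. The present point does not touch this calculation.

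**What is known at one year for each way out of Stage 2.**

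- Confirmed failure: status known; nothing is lost.
- One year reached with a working fistula: status known under the Section 10 narrative, but the table has no closing entry for it. A dated visit could fall under the clinic visits column; nothing requires one.
- Monitoring judged no longer necessary before one year: status unknown from exit onward.

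**Size of the gap.** Let N be the cohort, m the matured fistulas, and u those of the m that exit with unknown status. Assume that failures are known and that every matured fistula still followed stays patent. Then one-year patency lies between (m - u)/N, if all u are lost, and m/N, if all u are patent. The width is u/N.

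With N = 60, m = 0.78 × 60 = 46.8, rounded to 47:

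| Assumed share exiting | u | Lower bound | Upper bound |
|---|---|---|---|
| 10% | 5 | 42/60 = 70% | 47/60 = 78% |
| 25% | 12 | 35/60 = 58% | 78% |
| 50% | 24 | 23/60 = 38% | 78% |

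With N = 45 (after dropout), m = 35 and u = 4, 9 or 18, the lower bounds are 69%, 58% and 38%, and the upper bound is again 78%.

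**Calendar.** Taking 1 May 2020 to 31 December 2021, the window is 609 days, or 20.0 months; ending on 1 December it is 19.0.

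- Enrolment period read as accrual: 365 + 364 = 729 days, or 24.0 months, for Stage 2 alone. The last 52-week exit depends on when Stage 2 opens:
  - With Stage 1 (1 May 2020): last entry 1 May 2021, last exit 30 April 2022, about 4 months past the projected end.
  - At the close of Stage 1 enrolment (1 November 2020): last exit 31 October 2022, about 10 months past.
  - After a further 24 weeks (18 April 2021): last exit 17 April 2023, about 16 months past.
- 'Until then' read as one 12-month period shared by enrolment and follow-up: 6 + 12 = 18 months, which fits. But a patient enrolled on day t of that period has only 365 - t days, so only those enrolled at the very start reach 52 weeks.

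**The case against.** Several points on the other side stand. The Stage 2 narrative in Section 10 does provide for following a working fistula to one year. Cumulative patency can be estimated with censoring, and Section 5 speaks of patency over a period of up to a year. The redacted Stage 2 text in Section 8 may contain an analysis, so the absence of a visible one is not counted against the plan. Records may allow later retrieval. The dates are labelled projected, expected or estimated. None of this supplies a planned status check after early exit, and an analysis method cannot restore status that was not collected.

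A reader might infer more than the documents support:

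- *That every patient starting dialysis leaves Stage 2, so most of the cohort loses one-year status.* The table column serves both stages and matches the Stage 1 rule. The Stage 2 text in Sections 7 and 10 never makes dialysis start an exit.
- *That censoring is certainly informative.* The Follow Up entry ties follow-up to maturation, but also to the surgeon's standard practice, and is not specific to Stage 2. 'May be' is as far as it goes.
- *That, if the enrolment period means time on study, all patients would have to accrue in two months or so.* That needs fully sequential stages and a full 24 weeks for the last Stage 1 patient (609 - 168 - 364 = 77 days). If Stage 2 opens when Stage 1 accrual closes, 609 - 364 = 245 days, about 8 months, are available.
- *That the calendar leaves the primary maturation comparison underpowered.* Nothing says that enrolment stops in December 2021.

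**Conclusion.** The point holds for the secondary endpoint. As written, the plan does not secure one-year patency status for the whole Stage 2 cohort: non-failed fistulas may exit at the surgeon's discretion, no later check is planned, and the schedule table has no 52-week entry to match the one-year end named in the narrative above it. Following the plan exactly could leave the endpoint incomplete and open to bias in either direction.

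The size is not determinable from the documents. The uncertainty in the patency figure equals the share of the cohort that exits with unknown status: about 8, 20 or 40 percentage points in the three assumed cases. These rest on the plan's 78% and on the simplifying assumptions above.

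The dates are an item to reconcile, not a demonstrated error. One reading overruns the window; the shared-period reading fits it but leaves almost nobody with a year of follow-up. No effect on the primary comparison or its power is claimed. This should be corrected, and the correction is cheap.

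**What to change.** 1. Separate stopping EchoSure scans from leaving the study. The surgeon's decision on scans is unchanged.
2. For Stage 2 patients whose scans stop without failure, record patency status and the date of any loss at week 52 from the chart or dialysis-unit record. First check that the consent wording, which is a separate document (Section 14.1), covers this.
3. Add a 52-week patency entry to the Section 10 table, and make Sections 3, 7 and 10 state the same end of follow-up, including the stage label on the second Treatments paragraph.
4. Unless the redacted Stage 2 text already gives an analysis, estimate cumulative patency by Kaplan-Meier, censoring only at true loss to follow-up or administrative end and not at the end of scanning.
5. State what 'enrollment period' and 'until then' mean. Then restate either the projected final exit or the endpoint, as patency at the follow-up the calendar allows.

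The cost is a protocol amendment, one record check per such patient, and possibly consent wording; no added procedure or patient. If the enrolment period means accrual, there is also a choice between a later projected end (about 4, 10 or 16 months, depending on when Stage 2 opens) and a shorter patency claim.

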6. STUDY DESIGN

This is a prospective, single arm, non-randomized, multi-center observational study to record objective data in patients undergoing upper extremity arteriovenous fistula construction with autologous tissue for the purpose of eventual hemodialysis access, in whom the EchoMark implantable marker is placed at the site of vascular anastomosis and the EchoSure module is used to collect ultrasonic data.

The expected duration of this study will be from May 2020 to December 2021. Patients will be identified and recruited by the surgeons participating in the study, who will be determined at a later date. Patients who have been scheduled for creation of an upper extremity autologous arteriovenous fistula creation surgery will be identified as appropriate for study recruitment. The study details will be explained to identified patients and the consent process will begin for willing patients. Participants in the study will have EchoMark devices implanted at the time of the surgery. Monitoring of fistulae will be performed in the postoperative period. Patients who wish to terminate their participation in the research will no longer receive EchoSure ultrasound examinations of their fistula and will revert to the standard monitoring practice of their surgeon.

Stage 1: Patients will be monitored using the EchoSure ultrasound to collect data. Data will be analyzed in an attempt to formulate normative ranges for relevant variables such that clear, objective metrics consistent with healthy versus pathologic fistula healing are established.

Stage 2: Patients will be monitored via EchoSure ultrasound in addition to the standard of care currently followed by the surgeon. Decisions will be made by the vascular surgeon, using a combination of clinical data and the EchoSure data to determine if and when interventions need to be made to prevent failure of fistula maturation. We will then calculate the effect of the EchoMark and EchoSure on the rate of successful fistula maturation.

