For this portion of the study, we will recruit an additional 60 patients planning to undergo elective construction of upper extremity autogenous hemodialysis access. Again, the EchoMark fiducial marker will be inset at the time of fistula creation. The minimum sample size of 45 (60 prior to 25% dropout factor) is powered to detect an approximate 25% reduction in all-cause fistula failure in the early postoperative period. A χ^2 power analysis was performed with $\alpha = 0.05$, $\beta = 0.8$ and standard-of-care fistula maturation success at 50% based on institutional experience and prior literature which ranges from 30-70% and EchoSure early intervention success based on the Muray-Cases results which showed a 78% success rate achieved by a novel program of pre-maturation ultrasonography and early intervention.

The nominal-by-interval association coefficient, Eta, will be calculated to determine the correlation between successful, unassisted maturation and EchoSure-derived values for flow and conduit diameter at two weeks. This will be compared to the similar findings of stage 1 using Student's t-testing and will validate the early maturation criteria derived from there. The association coefficient will be calculated to determine the correlation between successful, assisted maturation and EchoSure-derived values for flow and conduit diameter immediately following intervention. Pearson's correlation will be performed on both EchoSure-derived and Duplex-derived values of volumetric flow and conduit diameter to determine correlation between findings immediately following intervention and those at six weeks. [REDACTED]

Using χ^2 testing between the stage 1 and 2 cohorts, the benefit to maturation success of intervention based on early postoperative EchoSure examination will be determined.

9: PATIENT ENROLLMENT AND CONSENT

Method of Subject Identification and Recruitment

Patients will be identified and recruited by the surgeons participating in the study. Patients who have been scheduled for a fistula creation surgery will be identified as appropriate for study recruitment. The study details will be explained to identified patients and the consent process will begin for willing patients.

Informed Consent

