Written informed consent, in accordance with applicable international standards and trial center regulations, shall be obtained from each subject, prior to the trial procedures. The investigator retains a copy of the signed informed consent document in each subject's record, and provides a copy to the subject.

The Investigator must obtain the written informed consent of all subjects, and must not allow any subject to participate in the investigation prior to obtaining governing institutional review board (IRB), research ethics board (REB) approval, or Ethics Committee (EC) approval. Before starting the trial, the investigator provides the trial Sponsor with a copy of the sample Informed Consent document approved by the IRB, REB, or EC with documented evidence that the IRB, REB, or EC approved the protocol and the informed consent.

Process of Consent

Patients eligible for the study will receive detailed written information on the trial, after which they will be asked to give *written* informed consent in accordance with the local clinical site's Ethics Committee. **Oral consent is not an acceptable substitute.**

Consent may only be obtained in person by a member of the study team delegated with consenting responsibilities. Consent will be obtained by a member of the research team in the patient's preoperative visit to clinic or in the pre-operative area prior to the initiation of anesthesia. The research team will take as much time as necessary to confirm full understanding of the study in the consent discussion. There will be sufficient time for the patient to consider the

study obligations and decide whether or not to participate, as study participation will not change clinical care and their data can be removed at any time if they choose to disenroll. Participation is fully optional.

Study personnel should explain that even if a patient agrees to participate in the study and signs the ICF, the patient may not be eligible to participate if he/she fails additional eligibility criteria or the surgical plans changes during the procedure.

Once signed, a copy of the Patient Informed Consent document and the Patient Information Sheet will be given to the patient.

A Screening and Enrollment Log will be maintained in the on-site clinical records located at the study site to document select information about candidates who are enrolled in the study as well as those who fail to meet the entry criteria.

Vulnerable Subjects

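### Entry rests on an undefined surgeon judgement, worded differently in Sections 3 and 7, which leaves the Stage 1 versus Stage 2 comparison open to selection bias

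*Combined protocol and SAP*

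**What the plan says.** The same inclusion criterion appears twice, with different thresholds. Section 7 (Inclusion Criteria) takes patients "where the surgeon has selected EchoMark and EchoSure as the optimal method of vascular monitoring based on clinical assessment and plan". Section 3 (Inclusion Criteria) takes patients "where the surgeon selects EchoMark and EchoSure as an appropriate method of monitoring". Neither section says how the judgement is made, and the criterion is the same for both stages.

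On recruitment, Section 9 says "Patients will be identified and recruited by the surgeons participating in the study", and then "Patients who have been scheduled for a fistula creation surgery will be identified as appropriate for study recruitment"; Section 6 has near-identical wording. Neither section asks for consecutive patients. The Screening and Enrollment Log in Section 9 covers candidates who are enrolled "as well as those who fail to meet the entry criteria". No use of the log in the analysis is stated.

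On design and analysis, Section 6 states: "This is a prospective, single arm, non-randomized, multi-center observational study". Section 10 has Stage 2 apply the values obtained from Stage 1, so Stage 2 is enrolled later. Section 8 (Stage 2) describes the test of benefit in a sentence that begins: "Using χ^2 testing between the stage 1 and 2 cohorts, the benefit to maturation success of intervention based on early postoperative EchoSure examination will be". The readable text of Section 8 contains no matching, stratification, covariate adjustment or comparison of baseline case mix. Part of that section is redacted, including a passage just before this sentence, so some analysis detail may exist that cannot be seen.

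**The concern.** Appropriate and optimal are different thresholds: a surgeon could find the devices appropriate for many patients and optimal for few. Sites working from the summary and sites working from Section 7 could enrol different patients.

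The larger matter is the undefined judgement itself. It is made by the people who recruit, and it is made twice: once for the Stage 1 cohort, and again for the Stage 2 cohort by surgeons who may by then know which kinds of patient did well or badly. If that experience changes whom they select, the two cohorts differ in prognosis before EchoSure has any influence on care, and an unadjusted chi-square cannot separate the two. The protocol itself shows that case mix matters. Section 4 gives distal radiocephalic fistulas a historical maturation failure rate of 50-70%, and Section 8 puts standard-of-care success anywhere from 30% to 70%. A modest change in who enters could therefore pass for a device benefit, or hide one.

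**Working it through.** **Inputs from Section 8.** Stage 1 (standard-of-care) success 50%; Stage 2 success 78%; alpha 0.05; the stated beta of 0.8 read as power 0.80; 45 evaluable per stage; 25% dropout. Sidedness is not stated.

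**Step 1: reproduce the planned size.** Two-sided pooled chi-square formula without continuity correction:

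n = [1.960·√(2·p̄·(1−p̄)) + 0.842·√(p1(1−p1) + p2(1−p2))]² / (p2−p1)²

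With p1 = 0.50, p2 = 0.78 and p̄ = 0.64:

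- first term: 1.960 × √0.4608 = 1.330
- second term: 0.842 × √0.4216 = 0.546
- n = (1.877)² / 0.0784 = 44.9, so 45 per stage
- 45 / (1 − 0.25) = 60 recruited

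The plan's figures reproduce, with power 80.1% by formula. They are not in dispute here.

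**Step 2: the test that will be applied.** With x successes of n in Stage 1 and y of n in Stage 2:

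Z = [(y−x)/n] / √[p̄(1−p̄)·2/n], where p̄ = (x+y)/(2n)

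A result is significant in favour of Stage 2 when Z exceeds 1.96. For example, if Stage 1 gives 22 of 45, then 31 of 45 in Stage 2 is not enough (0.200/0.1037 = 1.93), but 32 of 45 is (0.222/0.1033 = 2.15).

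**Step 3: no device effect, but a shift in the Stage 2 baseline.** The probability is the sum, over all (x, y) meeting that condition, of Bin(x; n, 0.50) × Bin(y; n, p2). This is an exact enumeration. The documents give no size for any shift, so the p2 values are assumptions. The largest is the top of the protocol's own 30-70% range.

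| Stage 2 baseline | 45 per stage | 60 per stage |
|---|---|---|
| 50% (no shift) | 2.3% | 2.7% |
| 55% | 6.3% | 8.5% |
| 60% | 14.7% | 20.4% |
| 65% | 29.1% | 39.2% |
| 70% | 48.9% | 61.8% |

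More patients do not help: the probabilities are higher with 60 per stage.

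**Step 4: what such a shift would require.** Suppose, purely for scale, that candidates were of two kinds, with 70% and 30% success, mixed equally in Stage 1: 0.5 × 0.70 + 0.5 × 0.30 = 50%. A 55% baseline then needs 62.5% of the first kind (0.625 × 0.70 + 0.375 × 0.30 = 0.55), a 60% baseline needs 75%, and a 65% baseline needs 87.5%.

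**Step 5: the other direction.** If surgeons enrol harder cases in Stage 2, so that a true 78% becomes 68%, exact power with 45 per stage falls from 80.9% to 40.5%.

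**The case against.** The strongest reply is that one criterion governs both stages, so nothing in the text makes the cohorts differ. That stands against any claim that the comparison is biased. It does not remove the opening, because an undefined judgement can be applied differently at two times under the same words.

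A reader might infer that surgeons will use the Stage 1 criteria to choose Stage 2 patients. The documents do not support this. Those criteria rest on flow and diameter two weeks after surgery (Section 8), whereas consent is taken before anesthesia (Section 9). Nor can a surgeon favour a lesion that looks correctable in a fistula not yet created. What remains is general experience of which patients did well in Stage 1.

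A reader might also see a third population in Section 6, where patients are recruited once scheduled for surgery: "Patients who have been scheduled for creation of an upper extremity autologous arteriovenous fistula creation surgery will be identified as appropriate for study recruitment". That sentence describes a recruitment pool, later narrowed by the criteria, which is ordinary. The inconsistency is between Sections 3 and 7.

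It is tempting, too, to say that the log would reveal nothing. In fact a screened candidate whom the surgeon does not select has failed an inclusion criterion and falls within the log. The gap is scheduled patients who were never approached, and the lack of any requirement to record the surgeon's reason.

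Two further objections have force. Any non-randomised comparison is sensitive to baseline shift, so the figures show vulnerability and not that this clause causes a shift. And leaving device use to the surgeon fits an observational study in which, according to Section 9, taking part does not alter clinical care. That second point limits how far the criterion can be changed without other edits.

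**Conclusion.** The point holds as a vulnerability that the plan can reduce cheaply. Sections 3 and 7 must be reconciled in any case, although the difference in wording does not by itself create a difference between stages. What leaves the comparison open to selection bias is the combination of an undefined judgement, recruitment by those who make it, no consecutive enrolment, sequential cohorts and an unadjusted test.

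Neither the direction nor the size can be known from the documents. For scale, with no device effect, assumed baseline shifts of 5, 10 and 15 points raise the chance of a significant result favouring Stage 2 from 2.3% to 6.3%, 14.7% and 29.1%. A 10-point shift the other way halves the power. These figures assume 45 evaluable per stage, Stage 1 success of 50%, a two-sided 5% Pearson test without continuity correction, and no adjusted analysis behind the redactions.

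A reader might add the loss of power that would follow if EchoSure findings guided care in Stage 1 and raised its success rate. That would be contamination of the comparator and not selection. Section 6 describes EchoSure-informed decisions only for Stage 2.

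**What to change.** 1. Replace the clause in Sections 3 and 7 with one objective criterion, identical in both stages and not dependent on the surgeon's preference for EchoSure. Being scheduled for elective upper-extremity autologous fistula creation, together with the remaining listed criteria, would serve.
2. In Sections 6 and 9, require the study to be offered to consecutive eligible scheduled patients.
3. Extend the Section 9 log to scheduled patients never approached or not selected, with fistula type and reason.
4. In Section 8, prespecify reporting of the enrolled fraction and baseline case mix by stage and site, and add a supporting between-stage analysis adjusted for fistula type.
5. State as limitations that unrecorded selection and calendar-time differences between the stages would remain; adjustment for recorded factors does not remove them.

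The cost is protocol wording, a few more log entries per site and some loss of surgeon discretion. That loss has to be squared with the observational description in Section 6 and the consent statement in Section 9 that participation does not change care. If the surgeon-choice clause must stay for that reason, a single wording, the fuller log and the reporting in items 3 to 5 still apply.
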